8.1.1. Primary Analysis

Change from baseline in sleep disturbance score will be analyzed on the ITTp population using a MMRM approach under the Missing at Random (MAR) framework. The MMRM model will include study intervention (Dupilumab, Placebo), age, BMI, stratum (Eastern Europe with high ICS dose, Eastern Europe with medium ICS dose, rest of world [ROW] with high ICS dose and ROW with medium ICS dose), inclusion in [REDACTED], visit (up to Week 12), study intervention-by-visit interaction, baseline ACQ-5, baseline sleep disturbance score and baseline-by-visit interaction as covariates.

An unstructured correlation matrix will be used to model the within-participant errors covariances. The Kenward-Roger approximation (**ddfm=kr**) will be used to estimate the denominator of degrees of freedom. Parameters will be estimated using restricted maximum likelihood method with the Newton-Raphson algorithm. The adjusted least square (LS) mean in change from baseline of each study intervention group, the LS means difference between the dupilumab and placebo groups, and the corresponding SEs and 95% CI will be provided at all scheduled visits. The p-value corresponding to the LS mean difference will be provided at Week 12 only. For participants discontinuing the study intervention before Week 12 not due to the COVID-19 pandemic, off-study intervention sleep disturbance scores measured up to Week 12 will be included in this analysis. In contrast, for any participants discontinuing the study intervention due to the COVID-19 pandemic, off-study intervention data will not be included (i.e., set to missing) but will be assumed missing at random.

If the MMRM model under unstructured correlation matrix fails to achieve convergence due to complexity of model specification, different covariance structures will be used according to the following order till convergence is achieved:

1. Heterogeneous Toeplitz (TOEPH)
2. Homogeneous Toeplitz (TOEP)
3. First-Order Autoregressive [AR(1)]
4. Compound Symmetry (CS)

8.1.2. Assumption Testing

No assumption testing will be performed.

8.1.3. Missing Data Handling

No imputation will be made for the missing values for the primary analysis, unless specified differently in the estimand strategy (see [Table 2-2](#)).

8.1.4. Subgroup Analysis

Primary analysis will be replicated for the following subgroups:

- Age category (≥ 18 to <40 , ≥ 40 years)
- Gender (Male, Female)
- Race (Not-White, White)
- Baseline body weight (<70 , ≥ 70 to <100 , ≥ 100 kg)
- Region (Eastern Europe, ROW)
- Participants who had concomitant SCS rescue medications (identified with file provided by Sanofi containing CDGsn00010 medications) (Yes, No)
- Baseline ICS dose level (Medium, High)
- Age of onset of asthma (<18 , ≥ 18 to <40 , ≥ 40 years)
- Number of severe asthma exacerbation events (1, 2, >2) within 1 year prior to the study
- Number of controller medications at study entry (2, 3)
- Smoking history (Former, Never)
- Baseline [REDACTED] [REDACTED]
- Baseline Eosinophils (<300 , ≥ 300 cells/uL)
- Baseline ACQ-5
 - (≤ 3 , >3)
 - (≤ 3.5 , >3.5)
- Participants with > 2 weekly average nocturnal awakenings at baseline (Yes, No)
- Participants with Chronic rhinosinusitis with nasal polyps (CRSwNP) co-morbidities (Yes, No)

In these subgroup analyses, nominal p-value will be provided for descriptive purpose only.

Results will also be illustrated with forest plots.

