## 2 INTRODUCTION

Asthma is a chronic inflammatory disease of the airways characterized by airway hyperresponsiveness, acute and chronic bronchoconstriction, airway edema, and mucus plugging. The inflammatory component of asthma involves many cell types, including mast cells, eosinophils, T-lymphocytes, neutrophils, and epithelial cells and their biological products. For most asthma patients, a regimen of controller therapy and reliever therapy provides adequate long-term control.

Respiratory disturbances during sleep are recognized as extremely common disorders with important clinical consequences in patients with asthma. Difficulties inducing sleep, sleep fragmentation, early morning awakenings, and daytime sleepiness are more common in subjects with asthma compared with subjects without asthma (13).

Dupilumab, a fully human monoclonal antibody, is directed against the IL-4R $\alpha$  subunit, which is a component of IL-4 heterodimeric receptors Type I (IL4-ligand only) and Type II (both IL-4 and IL-13 ligands). The binding of dupilumab to IL-4R $\alpha$  results in blockade of downstream signaling initiated by both IL-4 and IL-13. These cytokines play key roles in the pathogenesis of various allergic diseases including asthma (14). The results of dupilumab pivotal studies have demonstrated its efficacy in moderate-to-severe asthma patients by decreasing the rates of severe asthma exacerbation, improving the lung function and asthma control (15), reducing oral glucocorticoid use (16) as well as decreasing disturbance measured by evening symptom score and nocturnal awakening.

Dupilumab is approved in the US for use in adults and adolescents ( $\geq 12$  years) with moderate-to-severe eosinophilic asthma and in the European Union (EU) for use in adults and adolescents ( $\geq 12$  years) with severe asthma with Type 2 inflammation. In Japan, dupilumab received Pharmaceuticals and Medical Devices Agency (PMDA) approval for use in adults and adolescents ( $\geq 12$  years) with severe or refractory bronchial asthma.

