#### Type of participant and disease characteristics

I 02. Participants with a physician diagnosis of asthma based on the Global Initiative for Asthma (GINA) 2020 ([27](#)) for  $\geq 12$  months treated with medium to high dose ICS and a second controller (ie, LABA, LTRA). A third controller is allowed but not mandatory. The dose regimen should be stable for at least 1 month before SV1 and during the screening period.

I 03. History of at least one severe asthma exacerbation within 1 year prior to SV1. Severe exacerbation is defined as deterioration of asthma that results in emergency treatment, hospitalization due to asthma, or treatment with systemic steroids (oral or injectable).

I 04. Participants with eosinophils  $\geq 150$  cells/ $\mu$ L and FeNO  $\geq 25$  ppb during screening, prior to randomization.

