### Prohibited concomitant therapy:

- Any biologic therapy (including experimental treatments) or systemic immunosuppressive drugs.
- Treatment with systemic corticosteroids (systemic corticosteroids can only be used to treat a severe asthma exacerbation and are not allowed to be used for other conditions).
- Treatment with live (attenuated) vaccine.
- Sedative, anxiolytic, or hypnotic treatments including melatonin.
- Antihistamines, except the newer generations of antihistamines (eg, cetirizine, loratadine and fexofenadine).
- Theophylline.
- Lipophilic beta blockers, opioids, clonidine, antidepressants or other medications known to interfere with sleep, as determined by the Investigators.

Note: In most cases, chronic treatments administered regularly and at stable dosing are acceptable. Investigators should assess the degree to which an individual medication may cause changes in sleep pattern or sleep quality during the study, compared to the prebaseline state.

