### 6.5.1 Rescue medicine

The SABA rescue medications may be used. The rescue medication will be administered as prescribed by the physician. Systemic corticosteroids are allowed for the treatment of severe asthma exacerbations.

Although the use of rescue medications is allowed at any time during the study, every attempt should be made to perform all necessary measurements prior to the use of rescue medications. If SABA rescue medications are given prior to [REDACTED] or spirometry, the measurements should be performed after a wash-out time mentioned in [Table 4 \(Section 8.1.3\)](#). The date and time of rescue medication administration as well as the name and dosage regimen of the rescue medication must be recorded.

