7.1.2. Concomitant Medications

Concomitant medications are any treatments received by the participant concomitantly to the IMP, starting from the date of 1st administration of IMP to the date of last administration + 14 days (boundary included).

The following concomitant medications summaries will be generated separately by study intervention group:

- Inhaled corticosteroids in combination with other controllers summarized by medication type (ICS, LABA, LAMA, LTRA, Other) and standardized medication name.
Note: These medications are recorded in the Asthma controller medication eCRF page and ATC codes will be used to categorize them into ICS (ATC class R03BA), LABA (ATC class R03AC), LAMA (ATC class R03BB), LTRA (ATC class R03DC) or Other.
- Reliever (rescue) medications summarized by medication type (SABA, systemic corticosteroids, other) and standardized medication name (see [Section 15.10](#)).
Note: These medications are recorded in the Asthma reliever medication eCRF page.
- Other concomitant medications.
Note: These medications are recorded in the Other medication eCRF page.

The concomitant prohibited medications will also be presented by prohibited medication category as defined in deviation and standardized medication name (see [Section 15.10](#)).

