7.1.3. Post-treatment medications

Post-treatment medications are those the participant took (continued or initiated) in the period running from the 15th day after the last administration of IMP up to the end of the study, based on Investigator's decision. Post-treatment medications will not be summarized or presented in the CSR.

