15.8. Participant-Reported Outcomes (PROs)

Asthma Sleep Disturbance Questionnaire

The Asthma Sleep Disturbance Questionnaire is a PRO measure designed to assess the impact of asthma on participants' sleep. Scores range between 0 to 4 with 0 indicating no impact of asthma on sleep and 4 indicating higher impact of asthma on sleep.

Participants will be instructed to record the severity of the disturbance of their sleep due to asthma as follows:

- 0 = Slept through the night, no asthma symptoms,
- 1 = Slept well, no nighttime awakenings because of asthma, but some asthma symptoms in the morning,
- 2 = Woke up once because of asthma (may or may not include early awakening),
- 3 = Woke up several times because of asthma (may or may not include early awakening),
- 4 = Bad night, awake most of the night because of asthma.

The participants will record their sleep disturbance in an electronic diary, once a day upon awakening.

Asthma Sleep Disturbance Questionnaire data will be provided by CLARIO.

ADSD and ANSD

ADSD and ANSD assess asthma severity based on participant self-report of asthma core symptoms (i.e., difficulty breathing, wheezing, shortness of breath, chest tightness, chest pain and cough).

Both ADSD and ANSD are composed of 6 items rated using an 11-point numeric rating scale (NRS) that ranges from 0 = None to 10 = as bad as you can imagine, which will be completed by participants daily for 11 days before Baseline visit and for 7 days prior each subsequent visit (every night before they go to bed for ADSD and every morning when getting up for ANSD, respectively).

ADSD and ANSD data will be directly provided by CLARIO.

PROMIS Sleep Related Impairment Short Form 8a

The PROMIS is a DSM-5, Level 2, sleep disturbance measure to assess the impact of sleep-related impairment during waking hours. This study uses the 8-item PROMIS Sleep Related Impairment Short Form (PROMIS SF v1.0 Sleep-Related Impairment Short Form 8a).

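### SAP 8.1.4 splits the primary analysis by systemic corticosteroid rescue use, a post-randomization factor that treatment can change, so neither subgroup contrast is protected by randomization

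*SAP*

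**What the plan says.** SAP 8.1.4 replicates the primary analysis in a list of subgroups, shows the results in forest plots, and gives nominal p-values for description only. One factor is "Participants who had concomitant SCS rescue medications (identified with file provided by Sanofi containing CDGsn00010 medications) (Yes, No"). Addendum #4 later replaced the coding file with ATC codes from the reliever page, but the subgroup remains. Addendum #17 lets levels be combined or modified, and it does not remove this row either.

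SAP 7.1.2 contains the SAP's only definition of a concomitant medication: "starting from the date of 1st administration of IMP to the date of last administration + 14 days". Addendum #12 extends the end of that window to last dose + 98 days. Section 8.1.4 cites neither.

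On the use of SCS, Protocol 6.5 states that "systemic corticosteroids can only be used to treat a severe asthma exacerbation and are not allowed to be used for other conditions", and 6.5.1 repeats that "Systemic corticosteroids are allowed for the treatment of severe asthma exacerbations". Protocol section 2 says dupilumab showed efficacy in its pivotal studies "by decreasing the rates of severe asthma exacerbation", among other effects.

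**The concern.** A subgroup contrast inherits the protection of randomization only if membership is fixed before treatment can act. Every other factor in 8.1.4 meets that condition: demographics, region, baseline weight and ICS dose, age at onset, prior-year exacerbations, controllers at entry, smoking history, baseline biomarkers and scores, and nasal polyp comorbidity. SCS rescue does not.

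Suppose dupilumab prevents some exacerbations. The dupilumab participants who still need SCS are then not comparable with the placebo participants who need them, and the same holds for those who do not. The forest plot would place these two estimates beside valid baseline subgroups with no warning about selection. Protocol 4.3 treats oral steroid use as a possible confounder of sleep outcomes, so a reader could easily take the SCS-No row as the steroid-free effect of dupilumab. It does not estimate that. What is at stake is the misreading of one descriptive pair of estimates.

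**Working it through.** **1. Is the factor post-randomization?** Yes. The concomitant window opens at the first dose in 7.1.2, and addendum #12 keeps that start.

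**2. Can treatment change membership?** Yes, on the protocol's own account. SCS is permitted only for severe exacerbations (6.5, 6.5.1), and section 2 says dupilumab reduces these.

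**3. Is membership plausibly related to the outcome?** Yes. Inclusion criterion I 03 states: "Severe exacerbation is defined as deterioration of asthma that results in emergency treatment, hospitalization due to asthma, or treatment with systemic steroids". The primary questionnaire (SAP 15.8) asks participants to "record the severity of the disturbance of their sleep due to asthma". Worsening asthma can drive both.

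**4. Does anything in the plan cure this?** No. Descriptive p-values concern multiplicity. Addendum #4 concerns identification, and addendum #17 concerns small levels. None addresses selection.

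**5. How large could the bias be?** The plan has no figure on this point to reproduce, and the documents give no SCS rate or correlation. All of the following inputs are assumptions:

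- Latent severity u. Baseline score, baseline ACQ-5 and outcome each equal 0.7u plus noise, with unit variance.
- SCS liability correlated rho with u, with arm-specific cut-offs giving the stated SCS rates.
- No treatment effect on the score.
- Treatment coefficient from a linear model within each level, adjusted for baseline score and ACQ-5.
- Standard errors scaled to the planned 117 evaluable per arm. There are 12 million simulated participants per scenario.

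| SCS placebo/dupilumab | rho | SCS-Yes bias (SE), in SD | SCS-No bias (SE), in SD |
|---|---|---|---|
| 10%/5% | 0.3 | 0.024 (0.416) | 0.006 (0.112) |
| 15%/7% | 0.3 | 0.028 (0.348) | 0.010 (0.114) |
| 25%/10% | 0.3 | 0.037 (0.284) | 0.017 (0.119) |
| 10%/5% | 0.6 | 0.053 (0.411) | 0.013 (0.112) |
| 15%/7% | 0.6 | 0.063 (0.345) | 0.020 (0.114) |
| 25%/10% | 0.6 | 0.086 (0.283) | 0.035 (0.119) |

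Positive values count against dupilumab. The third decimal is within simulation error in SCS-Yes. With rho = 0 the bias is 0.00 throughout. The bias is about 0.06 to 0.30 SE, so a nominal 95% interval would exclude zero in about 5.0% to 6.1% of trials.

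A second model has no covariate adjustment. The outcome correlates r with the SCS liability, and each arm has its own rate p and cut-off c:

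- SCS-Yes bias = r × [φ(c_d)/p_d − φ(c_p)/p_p]
- SCS-No bias = −r × [φ(c_d)/(1−p_d) − φ(c_p)/(1−p_p)]

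For 20% placebo, 10% dupilumab and r = 0.4, these are 0.4 × (1.755 − 1.400) = 0.14 SD and −0.4 × (0.195 − 0.350) = 0.06 SD. Over rates of 10%/5% to 30%/15% and r of 0.2 to 0.6, the ranges are 0.06 to 0.24 SD and 0.02 to 0.13 SD. With equal rates and the same cut-off in both arms, both are zero.

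**6. How many would be in SCS-Yes?** Using the rates in the table, 117 × 0.10 + 117 × 0.05 ≈ 18, and 117 × 0.25 + 117 × 0.10 ≈ 41. After addenda #13 and #14 the three-visit MMRM has 14 fixed effects: intercept 1, treatment 1, age 1, BMI 1, region 1, ICS 1, visit 2, treatment-by-visit 2, ACQ-5 1, baseline 1, baseline-by-visit 2. The unstructured covariance adds 3 × 4/2 = 6 parameters.

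**7. Which window applies?** SAP 7.1.3, not amended, treats as post-treatment, and does not present, any medication taken "in the period running from the 15th day after the last administration of IMP up to the end of the study". Compare this with the last dose + 98 days of addendum #12 and planned follow-up of at most 84 days after the last dose:

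| Last dose | +14 days | 7.1.3 starts | Planned follow-up ends | +98 days | Days with both labels |
|---|---|---|---|---|---|
| Day 85 | 99 | 100 | 169 | 183 | 100–169 |
| Day 71 | 85 | 86 | 155 | 169 | 86–155 |

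Under addendum #12, SCS first taken after the Week 12 visit (target Day 85) could place a participant in SCS-Yes.

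**The case against.** The strongest reply is that this is a labelling matter. The p-values are already declared descriptive, the row is outside the hierarchy, and under the adjusted illustration the bias is small against noise. That stands as to size. It does not make the two contrasts interpretable, because the descriptive label says nothing about selection.

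The illustrations rest wholly on assumptions, and the two models differ in size. That also stands. Section 2 of the protocol refers to the pivotal studies, and no 12-week SCS rate is given. If treatment left SCS use and its selection mechanism unchanged, there would be no bias, but the protocol's own rationale points the other way.

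Some objections to the side points are right. With a last dose at Day 85, the 14-day window also runs past Week 12 (to Day 99), so addendum #12 widens that problem rather than creating it. The overlap with 7.1.3 is a drafting matter. SAP 3.1 plans two database locks, and membership could differ between them, but the SAP does not say that this subgroup analysis will be rerun.

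Finally, steroid use is a legitimate interest given Protocol 4.3, and the 8.1.6 analysis that sets scores after SCS intake to missing answers a different question. This is an argument for keeping the information in a correctly labelled form. It does not justify keeping the row among the baseline subgroups.

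**Conclusion.** The concern holds. Concomitant SCS rescue is the only factor in 8.1.4 defined after the first dose. The protocol gives reason to expect treatment to change it, and nothing in the SAP or its addendum removes the resulting selection. Neither the SCS-Yes nor the SCS-No contrast estimates an effect in a population definable at baseline.

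The direction and size of the bias cannot be determined from the documents. Under the baseline-adjusted assumptions it is at most about 0.09 SD in SCS-Yes and 0.04 SD in SCS-No, and larger in the unadjusted model. The primary conclusion, the hierarchy and the type I error do not depend on it. It should be corrected because the correction is cheap, not because the trial's main result is at risk.

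**What to change.** Delete the concomitant-SCS factor from SAP 8.1.4 and from its forest plot. If the team wants to keep the information, take it out of the forest plot and show it in a separate table labelled as a non-randomized description, counting only SCS started up to the Week 12 visit.

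Keep the prior-year exacerbation subgroup, which is a baseline factor. Report SCS rescue by arm as an outcome through the reliever summary already planned in 7.1.2. For the influence of SCS on the primary score, rely on the 8.1.6 supplementary analysis in the full ITTp set, and repeat beside that result the missing-at-random assumption it takes from the primary model. Separately, reconcile 7.1.3 with addendum #12.

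The cost is one descriptive output lost, or one relabelled with one extra derivation flag. The other analyses are already planned.

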3.1. Overall Study Design and Plan

This is a Phase IV, 1:1 randomized, parallel, multicenter study, with a 12-week double-blind placebo-controlled treatment period to assess the effect of dupilumab in improving sleep outcomes, asthma control, and health related quality of life, and in reducing daytime and nighttime asthma symptoms.

Approximately 260 participants will be randomly assigned to study intervention in a 1:1 Dupilumab to placebo ratio to achieve 234 evaluable participants for an estimated total of 117 evaluable participants per study intervention group.

The study will comprise of:

- Screening Period 1 (Day -35 to -12 from signed informed consent): Participants will be evaluated according to inclusion and exclusion criteria
- Screening Period 2 (Day -11 to -1; pre-baseline assessments): eligible participants will complete the assessments specified in the schedule of activities (SoA).
If preferred by the participant and the investigator for logistical reasons, screening visit 1 and screening visit 2 can be merged into a single on-site visit which will have to be done on Day -11 at the latest
- Baseline (Day 1): Participants who remain eligible will be randomized
- Randomized double-blind placebo-controlled treatment period (12 weeks from baseline): Participants will be randomized to receive either Dupilumab or placebo
- Post-treatment follow-up period: up to 12 weeks after last dose of IMP or until the participant switches to commercialized dupilumab (or other biologic product), whichever comes first.

Study duration for each participant will be approximately 16 weeks and up to 29 weeks. A participant is considered to have completed the study if he/she has completed all phases of the study including the post treatment follow-up visit.

[figure not shown]
The end of the study is defined as the date of the last visit of the last participant in the study.

The study analysis will be conducted in two steps. A primary database lock will be performed when all randomized participants will have completed the Week 12 visit or will have discontinued the study. The database will be updated at the end of the study for all participants to include the post-treatment follow-up information and updates for the events previously ongoing at the time of the primary lock. The CSR will include analyses from both the primary database lock and the final database lock.

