4.1. Sample Size

The sample size was chosen to enable an adequate characterization of the efficacy between dupilumab 200 mg Q2W and placebo with regards to the primary endpoint, change from baseline in sleep disturbance score at Week 12 in participants with moderate to severe asthma.

The sample size calculation was based on the subset of adult participants who had more than 1 weekly average nocturnal awakening at baseline, baseline ACQ-5 ≥ 2.5 , baseline blood eosinophils ≥ 150 cells / μ L and baseline FeNO ≥ 25 ppb in the previous [REDACTED] evaluating efficacy of dupilumab for participants with moderate to severe asthma.

The observed treatment difference on mean sleep disturbance score of the dupilumab group with 200 mg Q2W dosing in [REDACTED] versus placebo at Week 12 was [REDACTED]. A conservative estimate was used that assumes the treatment difference to be [REDACTED] at Week 12. Assuming normal distribution of the change in sleep disturbance score, a common standard deviation (SD) of [REDACTED], which came from the observed data in [REDACTED], with 117 participants per group, the study would have 90% power to detect a mean treatment difference of [REDACTED] using a two-sided test with alpha=0.05 for change from baseline in sleep disturbance score at Week 12 in the dupilumab 200 mg Q2W group versus placebo.

Assuming a 10% dropout rate, approximately 260 participants will be randomly assigned to study intervention to achieve 234 evaluable participants for an estimated total of 117 evaluable participants per intervention group. In order to mitigate the risk of potential different responses based on the Sleep Disturbance Questionnaire before and after amendment 01, the primary analysis of change from baseline in sleep disturbance score will exclude the participants who use the original questionnaire at baseline. The number of participants randomized up to the implementation of this protocol amendment is limited (ie, ≤ 10); therefore, the study power can be preserved at $\geq 89\%$ and therefore no participant replacement is planned.

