9.6. Other Safety Data

Not applicable.

10. Pharmacokinetics

Pharmacokinetic parameters are not evaluated in this study.

11. Pharmacodynamics

Pharmacodynamic parameters are not evaluated in this study.

12. Interim Analysis

An interim analysis (IA) in the study is planned for the purpose of [REDACTED] when approximately 50% of participants (approximately 130 participants from the ITTp population and $n_1 = 117$ evaluable participants) have completed the Week 12 visit or discontinued the study. The sample size re-estimation is planned to mitigate risk of power loss in the primary MMRM analysis described in [Section 8.1.1](#), given the large variability of placebo effects observed in [REDACTED]. The IA will be performed according to the [REDACTED] summarized as follows:

- Let \tilde{n}_2 be the incremental sample size between Stage 1 and Stage 2 (viz., up to and after the IA, respectively), and the cumulative sample size up to and including Stage 2 (final analysis) be $n_2 = n_1 + \tilde{n}_2$.
- The sample size re-estimation will be performed based on the

- [REDACTED]
[REDACTED]
[REDACTED]
No additional IA will be performed in the case of sample size increase. The test statistic at the final analysis will not be adjusted, since no sample size increase is planned if that [REDACTED]
- There is no plan to stop the trial early for superiority at the IA, and therefore the type I error can be preserved in theory. To implement a conservative analysis, an administrative alpha of 0.001 will be spent at the interim and 0.049 will be reserved for the final analysis.

13. Changes in the Planned Analysis

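### SAP 8.1.4 prints a nominal p-value within each subgroup level but never estimates whether the treatment effect differs between levels

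*SAP*

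**What the plan says.** SAP 8.1.4 states "Primary analysis will be replicated for the following subgroups" and lists 17 splits: 16 legible and one redacted. They include region, ICS dose, eosinophils, two cuts of baseline ACQ-5, and use of systemic corticosteroid (SCS) rescue. It adds that "In these subgroup analyses, nominal p-value will be provided for descriptive purpose only", and that forest plots will be drawn.

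The model being replicated (SAP 8.1.1) has two interactions: study intervention by visit, and baseline score by visit. It reports the LS mean difference with SE and 95% CI at each visit, and a p-value at Week 12.

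The addendum returns to this area three times. Item 4 changes how SCS use is identified. Item 13 enters region and ICS dose as separate covariates in all MMRMs. Item 17 allows subgroup levels to be merged or altered in light of the data, and reduces prior exacerbations to two levels. None of them adds a treatment-by-subgroup term, and the protocol's statistical section has none. Formal testing is confined by SAP 8.2.13 to the primary endpoint, nocturnal awakenings and the PROMIS t-score.

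**The concern.** A subgroup display is read mainly to see whether the effect is similar across levels. A p-value computed inside one level asks something else: whether the effect is zero in that smaller sample. Two levels with the same true effect can easily fall on opposite sides of 0.05, because each holds only part of the sample.

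With 17 splits in the tables, readers are likely to meet significant and non-significant levels of the same factor side by side. They would have no printed contrast to tell them whether the difference exceeds chance. At stake is how the region, ICS dose, eosinophil and ACQ-5 results are read, not the trial's main result.

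**Working it through.** **Inputs.** The design is "with 117 participants per group, the study would have 90% power to detect a mean treatment difference", "using a two-sided test with alpha=0.05 for change from baseline in sleep disturbance score at Week 12" (SAP 4.1), with 1:1 allocation (SAP 3.1). The treatment difference and SD are redacted, so only the standardised effect can be recovered. Subgroup shares are not given, apart from the 25% cap on Eastern Europe (SAP 4.2), and are assumed below.

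**Reproducing the plan's figure.**
- Expected z = 1.960 + 1.282 = 3.242.
- Implied effect = 3.242 × √(2/117) = 0.424 SD.
- Putting it back: n = 2 × (3.242/0.424)² = 116.9, so 117 per group. This is a consistency check only, because the effect was solved from 117.
- 234/0.90 = 260 randomised, as stated.
- At the 0.049 left for the final analysis (SAP 12), power is 89.8%, so 0.05 is used below without material loss.

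**One factor, same true effect in both levels.** For a level holding a fraction f of participants, z = 3.242 × √f and power = Φ(z − 1.960). With powers p1 and p2, the chance that exactly one level has p<0.05 is p1(1 − p2) + p2(1 − p1).

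| Split | Power, smaller level | Power, larger level | Exactly one p<0.05 |
|---|---|---|---|
| 50:50 | 63.0% | 63.0% | 46.6% |
| 40:60 | 53.6% | 70.9% | 48.5% |
| 25:75 | 36.7% | 80.2% | 58.0% |
| 10:90 | 17.5% | 86.8% | 73.9% |

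For 25:75 in full: 0.367 × 0.198 + 0.802 × 0.633 = 0.073 + 0.508 = 0.580.

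**All 16 legible splits together.** After addendum item 17, 14 splits have two levels and 2 have three. A simulation of 4,000 trials per scenario used one common effect, a Week 12 z-test at 0.05 in each level in place of the MMRM, and correlation of 0 or 0.3 between factors. The two-level shares were either all 50:50 or unequal (smaller level 15-50%).

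| Scenario | At least one discordant split |
|---|---|
| 234 evaluable, design effect | 96-99% (mean 8-9 of 16 splits) |
| 468 evaluable (520 cap less 10%), unequal splits | 93-94% |
| 468 evaluable, all 50:50 | 77% |
| 234 evaluable, 1.5 × design effect, unequal splits | 92% |
| 234 evaluable, 1.5 × design effect, all 50:50 | 71% |
| 234 evaluable, no effect, unequal splits | 56% |

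At the planned size and design effect, estimates of opposite sign in at least one split occurred in 22-39% of trials. Most discordance is therefore low power and not reversal.

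**What an interaction test would do.** Under a common effect, 16 tests at 0.05 flag 16 × 0.05 = 0.8 splits on average. The chance of at least one flag is 1 − 0.95¹⁶ = 56% if the tests are independent (51-56% simulated). For a 50:50 split there are 58.5 participants per arm in each level, so the SE of the interaction is √(4/58.5) = 0.2615 SD. Power for a difference of 0.424 SD between levels is Φ(0.424/0.2615 − 1.960) = Φ(−0.339) = 37%.

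**The case against.** The SAP labels these p-values nominal and descriptive, and no decision rule uses them. A reader might infer that subgroup conclusions are to be drawn from them, or that the type I error is inflated. The documents support neither: SAP 8.2.13 keeps formal testing to three hierarchical endpoints, none of them a subgroup result. This objection stands.

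Nor is heterogeneity information wholly absent. The replicated analysis gives a difference, SE and CI per level. The levels of a factor contain different participants, so (d1 − d2)/√(SE1² + SE2²) can be worked out by hand. This also stands, but it leaves to the reader the one contrast that the display is consulted for.

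The proposed change does not make the discordance disappear. A 95% CI per level excludes zero in essentially the same cases as p<0.05. Interaction tests are weak and still produce a chance flag in about half of trials. The gain is a direct estimate of the difference and far fewer chance signals (about 0.8 against 8-9 of 16), not their removal.

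Small cells are partly handled: levels may be merged (addendum item 17), and simpler covariance structures are available if the model does not converge (SAP 8.1.1). Finally, separate fits are the natural reading of the section but are not spelled out, and the table and figure shells are in a separate document.

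**Conclusion.** The omission is real and minor. The plan reports, per level, a test of zero effect, and nowhere estimates whether effects differ between levels. At the planned size and implied effect, a single two-level factor looks discordant about 47% of the time at 50:50 and 58% at 25:75 when nothing differs.

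The 96-99% refers to at least one of 16 splits. It should not be read as the chance for any given factor, or as the chance of an apparent reversal of effect. It rests on a common effect near 0.424 SD, assumed subgroup shares and a single-visit approximation to the MMRM. It falls to 71-77% with a larger effect or sample if every two-level split is 50:50, which the Eastern Europe cap rules out for region. The two ACQ-5 cuts are one variable, so the 16 splits cover 15 distinct characteristics. The type I error, the estimand and the primary conclusion are untouched.

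**What to change.** For each baseline factor, fit one MMRM on all ITTp participants. To the primary model add subgroup, subgroup-by-visit, treatment-by-subgroup and treatment-by-subgroup-by-visit terms. The main effects of region and ICS dose are already in the model after addendum item 13.

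- Report the Week 12 difference and 95% CI in each level, and the Week 12 interaction estimate, 95% CI and nominal p-value.
- Drop the within-level p-values from tables and forest plots.
- Label the interaction results exploratory, and state that power is low and that about 0.8 of 16 splits would be flagged by chance.
- Leave SCS rescue use out of this set. It is observed after randomisation, and an interaction test does not make it interpretable as a subgroup.

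The cost is a few lines of SAP text and modest programming. The statistical price is that the pooled model assumes a common covariance matrix and common covariate effects across levels, which separate fits do not. If the sponsor prefers separate fits, the difference between levels and its CI can be computed from the planned estimates and SEs and printed beside them.
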